b) Emotional Distress: Subjects may potentially experience emotional distress as a result of participating in this study. The study procedures could potentially lead to emotional distress from discussing trauma histories during mental health assessments. Each subject will be closely monitored for emotional distress, suicidal ideation and homicidal ideation at screening and each study visit. If a subject becomes significantly distressed or their psychiatric symptoms worsen and intervention is deemed appropriate, they will be walked to the emergency psychiatry clinic (on site) for evaluation and treatment (including potential hospitalization). The study medication will be discontinued and they will be withdrawn from the study if the patient is hospitalized, or if medical and/or psychiatric issues take precedence over study participation.

c) Safety Plan: We will implement a rigorous safety plan that encompasses close monitoring and care of medical issues in this study. The conduction of safety monitoring includes the following procedures outlined in the Physician On-Call Cascade (please see below in Adverse Event and Safety Evaluation section). This study would be conducted under FDA IND # 114,799. We will follow all FDA guidelines for annual progress, adverse event, and other reporting procedures for this outpatient randomized control trial.

Adequacy of Protection from Risks

Physical Risk and Subject Safety Possible side effects from drawing blood (as mentioned above) will be attended to as usual in the phlebotomy laboratory. If a subject experiences serious adverse effects from the study medication, it will be discontinued and s/he will be withdrawn from the study. The subject will immediately be referred for appropriate evaluation and treatment. All serious adverse effects will be documented and reported as required by the FDA and local IRB committee.

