Patients must have clinical diagnosis of chronic low back pain. Pain must be present on most days for at least 6 months. The pain must be either restricted to low back or associated with radiation to the proximal portion of the lower limb only (Class 1 and 2 per Quebec Task Force on Spinal Disorders). Study candidates must not have: a) neurological radicular signs; b) presumptive compression of a spinal nerve root on a simple radiogram (that is, spinal instability or fracture); or c) compression of a spinal nerve root confirmed by specific imaging techniques (computerized tomography [CT], myelography, or magnetic resonance imaging [MRI]) or other diagnostic techniques (for example, electromyography). The above diagnosis shall be made by a study physician and will be based on history, and physical and neurological examination. In addition, absence of spinal fracture, spondyloisthesis grade 3 or 4, tumor, abscess or acute pathology in the low back/abdominal regional must be confirmed by historical record of imaging studies (any of the following: plain x-ray, CT, or MRI). As per the study physician's opinion, there must be no clinically significant change in the condition since the time of imaging. A study physician will review medical charts and interview patients to determine disease criteria.

Pregnenolone: Pregnenolone is available over-the-counter and sold as a dietary supplement in the U.S., and estimated to be used by thousands of people. It has a very favorable side effect profile among clinical studies conducted to date; please see Appendix 3 for recent pregnenolone safety data summary. Despite its ubiquitous availability as a dietary supplement, pharmacokinetic data for pregnenolone are limited. Please see also summary of pregnenolone in the PDR for Nutritional Supplements (attached). No serious adverse events have been attributed to pregnenolone to date.

Treatment Compliance

Compliance for each visit interval is defined as taking between 80% and 120% of the study drug prescribed for that interval. For subjects who demonstrate noncompliance, the PI and/or study coordinator will counsel patients on the importance of study drug compliance and drug accountability. Patients who miss more than 6 consecutive doses of medication or are less than 80% compliant will be withdrawn from the study.

The following procedures will be employed to assure appropriate drug accountability:

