11. All subjects who complete the entire study (6 visits total) will receive two follow-up phone calls during Weeks #7 and #8 and be asked about adverse events (Hillside Adverse Events) and suicidality (CSSRS).

ADVERSE EVENTS AND SAFETY EVALUATIONS

Adverse Events: Adverse events will be recorded by administration of the Hillside Adverse Event Form and reviewed by a study physician (please see physician study team schedule/cascade). Adverse events will be assessed at all study visits after the screening visit (i.e. Visits 2-6). In addition, adverse events will be assessed by a follow-up telephone call at the end of the study medication taper (Week 7) and again one week after study medication has been stopped (Week 8). In addition to receiving these regular adverse effect assessments, patients will be given a toll free study number that they can call if they have questions regarding the dose escalation schedule or medication side effects. They will also be provided with the cell phone number of the study PI, [name], PhD as well as [name], MD. Other covering VA physicians (as part of the call cascade) will be accessible to [name] as per the call schedule.

Suicidality Safety Procedures for Follow-Up Phone Calls:

If a participant reports suicidality (suicidal ideation, gesture, or attempt) as per the Columbia Suicide Severity Rating (CSSRS, which is an FDA-recommended assessment for suicidality in clinical trials) during any follow-up phone call, a study physician will be notified immediately to determine whether the situation requires immediate clinical intervention. If a participant is thought to be at imminent risk to self, he/she will be referred immediately to emergency psychiatric care at the Durham VA Emergency Department, to Psychiatric

Emergency Services (PEC) at the Durham VA, or to the participant's local Emergency Department for further evaluation. If the participant is unwilling or unable to get to emergency psychiatric care and appears to be in imminent danger of self-harm, the study team will contact local law enforcement who will follow up with the participant at their current location.

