Secondary analyses will include the following assessments. Assessment of changes in mood, anxiety, sleep, working memory, executive function, and pain interference (BDI, DTS, Tower of London, Digit Sequencing Task, BPI interference, PGI, AIS) will be analyzed via a repeated measures analysis similar to analyses for primary outcome assessments. Categorical analyses of patient response (30% improvement, 50% improvement) will be evaluated via a comparison of proportions using Fisher's exact test. Time to event analyses will also be performed, to examine the time to 30% and time to 50% reduction in 24 hour average pain score, using daily pain score data. These analyses will be performed by calculating Kaplan-Meier survival curves. Changes in physical function, mental health, cognitive symptoms and back pain-related disability will be assessed using ANCOVA models. Safety will be assessed by comparing the incidence of major and minor side effects (defined in human subjects section below) in the study drug vs. placebo groups, using Fisher's exact tests. Path analysis will be used to perform a preliminary assessment of whether any pain reduction effect is independent of possible effects of study drug on anxiety and mood.

Missing data: The mixed models used to evaluate the continuous response variables are able to handle moderate amounts of missing data provided they are missing at random. We will examine the missing at random

assumption by assessing differences between dropouts and completers on baseline as well as response variables up to point of premature withdrawal. If the missing at random assumption does not appear to be tenable, we will report the mixed models results but spend additional effort characterizing treatment effect at time of premature withdrawal.

[figure not shown]
Power Analysis and Sample Size Determination:

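### The Week 7 and Week 8 safety calls are assigned to subjects who complete all six visits, so subjects withdrawn early have no scheduled adverse-event or C-SSRS assessment after stopping drug

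*Combined protocol and SAP*

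**What the plan says.** **Who is called.** Study Timeline, item 11: "All subjects who complete the entire study (6 visits total) will receive two follow-up phone calls during Weeks #7 and #8". The calls cover adverse events (Hillside form) and suicidality (C-SSRS).

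**The other description of the calls.** The Adverse Events paragraph under Adverse Events and Safety Evaluations first covers the visits: "Adverse events will be assessed at all study visits after the screening visit (i.e. Visits 2-6"). It then says that "adverse events will be assessed by a follow-up telephone call at the end of the study medication taper (Week 7"), with a second call at Week 8. It states no completer limit.

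**Who leaves the study.**
- Adequacy of Protection from Risks: "If a subject experiences serious adverse effects from the study medication, it will be discontinued and s/he will be withdrawn from the study".
- Potential Risks, b) Emotional Distress: "they will be withdrawn from the study if the patient is hospitalized, or if medical and/or psychiatric issues take precedence over study participation".
- Treatment Compliance: "Patients who miss more than 6 consecutive doses of medication or are less than 80% compliant will be withdrawn from the study".
- Potential Risks, a) Physical Risk: a subject with side effects at any dose may have the dose reduced or may be withdrawn.

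**How safety is compared.** Statistical Methods, secondary analyses: "Safety will be assessed by comparing the incidence of major and minor side effects", by arm, with Fisher's exact tests. That text gives no observation window or denominator, and does not say whether events reported in the calls count.

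**The concern.** A subject qualifies for post-drug safety follow-up by reaching Visit 6, and the events that most call for such follow-up are among those that remove a subject before Visit 6. Two things are at stake.

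The first is monitoring. The Background describes a raised risk of self-harm in this population, and the protocol has a dedicated suicidality procedure for these calls. Yet a subject withdrawn for psychiatric reasons has no scheduled C-SSRS afterwards, while a completer has two.

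The second is the comparison of arms. If events after stopping are counted, the length of observation depends on what happened after randomisation, and may differ by arm.

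**Working it through.** **Step 1. Set the provisions side by side.**

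| | Completes Visit 6 | Withdrawn before Visit 6 |
|---|---|---|
| Scheduled adverse-event assessment on study | Visits 2 to 6 | Visits attended up to withdrawal |
| Scheduled adverse-event and C-SSRS assessment after stopping | Week 7 and Week 8 calls | None found |
| Other provisions | Toll-free number; serious adverse effects reported | The same, plus clinical referral |

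The Adverse Events paragraph does not fill the empty cell. It places the first call at the end of the taper, and the only taper described starts at Visit 6 (Dosing; Study Timeline, item 8). Vital status is sought only for subjects who revoke authorization (Privacy and Confidentiality).

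The gap is widest late in treatment. The last dose step starts at Visit 5 (Week 4), there is no Week 5 visit, and Visit 6 is at Week 6. A subject withdrawn between those visits has no scheduled adverse-event or C-SSRS assessment at any time after starting that step.

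**Step 2. How many subjects.** Research Design and Methods expects up to 120 randomised to obtain 45 per group.
- 120 − 2 × 45 = 30, and 30/120 = 25%. Equivalently, 90/(1 − 0.25) = 120, so the plan's figures are consistent with a 25% allowance.
- This is an upper limit. Subject Recruitment applies the same 120 to subjects enrolled, so part of the allowance may be lost before randomisation.

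**Step 3. When the comparison is biased.** Suppose post-stop events are counted over all randomised subjects. Per arm, let N be the number randomised, w the number withdrawn, q the post-stop risk in withdrawn subjects and c the risk in completers.
- Incidence with everyone followed: [(N − w)c + wq]/N
- Incidence seen with calls to completers only: (N − w)c/N
- Missed: wq/N

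The difference between arms (pregnenolone A minus placebo B) is understated by (w_A q_A − w_B q_B)/N. This is zero only when wq is equal in the two arms.

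The documents give no post-stop risks and no withdrawals by arm, so the values below are assumptions: N = 60, c = 5%, 30 withdrawn in total.

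| | w, A vs B | q, A vs B | Difference, all followed | Difference seen | Shift | Subjects with events missed, A + B |
|---|---|---|---|---|---|---|
| a | 15 vs 15 | 20% vs 20% | 0.0 | 0.0 | 0.0 | 3 + 3 |
| b | 20 vs 10 | 20% vs 20% | +2.5 | −0.8 | 3.3 | 4 + 2 |
| c | 15 vs 15 | 20% vs 10% | +2.5 | 0.0 | 2.5 | 3 + 1.5 |
| d | 25 vs 5 | 40% vs 20% | +13.3 | −1.7 | 15.0 | 10 + 1 |
| e | 10 vs 20 | 20% vs 20% | −2.5 | +0.8 | −3.3 | 2 + 4 |

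Differences and shifts are in percentage points. Row b in full:
- All followed: (40 × 0.05 + 20 × 0.20)/60 = 10.0% against (50 × 0.05 + 10 × 0.20)/60 = 7.5%.
- Seen: 2.0/60 = 3.3% against 2.5/60 = 4.2%.

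Row e shows that the shift can also go against pregnenolone. With completers as the denominator, the difference seen is zero in every row, because c is set equal in both arms.

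**Step 4. When it is not biased.** Suppose the endpoint is any side effect at any time and every withdrawal is for a side effect. Each withdrawn subject is then already counted. Adding completers' post-stop events, row b gives 20 + 40 × 0.05 = 22 of 60 against 10 + 50 × 0.05 = 12.5 of 60, whether or not withdrawn subjects are called.

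**The case against.** The strongest reply has four parts.

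**No bias is shown.** A reader might infer that the plan's safety comparison is biased in favour of pregnenolone. The documents do not support that. Statistical Methods does not say that Week 7 and 8 events enter the comparison, the event that triggers withdrawal can already be recorded, and visits before withdrawal count. Step 4 gives a case with no bias, and rows a and e of Step 3 give no shift and the opposite shift. Small reversals also change little: Fisher's test on 8 vs 7 of 60 and on 4 vs 5 of 60 gives p = 1.0 both times. This part stands, so the claim must be conditional. Bias remains possible for specific event types and for subjects withdrawn for reasons other than a side effect.

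**Withdrawn subjects are not without care.** A reader might infer that no safety information at all is planned once they stop. That is too strong. Serious adverse effects are documented and reported, patients have a toll-free number, distressed subjects are taken to on-site emergency psychiatry where intervention is judged appropriate, and those not in care are referred. This also stands. The gap is in scheduled assessment.

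**Not everyone with side effects is lost.** Subjects kept on a reduced dose can reach Visit 6 and be called. Correct, but serious adverse effects and hospitalisation lead to withdrawal.

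**The text may already cover it.** Item 11 does not contain the word only, and the Adverse Events paragraph names no completer limit. But both descriptions presuppose Visit 6 or its taper, so at best they conflict. Part of the safety section, apparently the physician on-call list, was not available for this review, and nothing here relies on its content.

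**Conclusion.** The point holds as a gap in scheduled safety assessment and as a wording conflict. In the text available, a subject withdrawn before Visit 6 has no scheduled adverse-event or C-SSRS assessment after stopping drug, while a completer has two.

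The statistical consequence is conditional. The between-arm comparison can be biased if post-stop events count and the product of withdrawal and post-stop risk differs between arms. Neither quantity is given, so the size is unknown. The 0 to 15 point range rests wholly on assumed rates, and the upper end needs a five-fold imbalance in withdrawals together with a doubled post-stop risk. Even with no bias, events go unseen: 6 expected in the balanced row a.

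A reader might take 25% of randomised subjects as the number affected. The documents support that only as a ceiling.

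Severity: should-fix. This is a pilot with safety as a secondary analysis, but the remedy is cheap and reaches the subjects most likely to have had a problem.

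**What to change.** 1. Amend Study Timeline item 11 and the Adverse Events paragraph to say the same thing: every subject who took at least one dose of randomised study drug is offered both calls (Hillside Adverse Event Form and C-SSRS), timed from the last dose, whatever the reason for stopping, subject to consent.
2. In Statistical Methods, state that the safety comparison uses all such subjects over a common window that includes both calls, and say how a subject with a missed call is counted.
3. Report by arm how many subjects completed each call, so that any remaining imbalance is visible.

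The rules on when drug is stopped or a subject is withdrawn are not part of this change.

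Cost: protocol wording, plus at most 30 × 2 = 60 extra calls at the 10 minutes each shown in the Study Schedule, which is 600 minutes or 10 hours over the trial. The forms, staff and suicidality procedure already exist. Some withdrawn subjects will not answer, so ascertainment will improve but will not be complete.

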There will be a master schedule available that adapts the above call-schedule to the annual leave and travel schedules of the individual MDs listed in this cascade. This on-call schedule will be circulated weekly, so that the order of the call cascade is always up-to-date for any particular week (and incorporates any changes that may be necessary secondary to individual MD schedules).

The designated physician on-call will have the following responsibilities: The designated study team MD will conduct physical exams at baseline and study completion, medical chart review, determination of patient eligibility for study entry, review of all clinical laboratory results and ECG tracings within 24 hours (with ECG confirmation by cardiologist [name]), assessments of potential side effects to study medication by reviewing a structured rating assessment administered to each research participant at each study visit and by interviewing and examining the participant as clinically indicated, and will attend to any other medical issues that arise during the course of this study.

Should any emergent issues arise that require immediate medical and/or psychiatric attention, patients will be walked to the Durham VA Emergency Department and Psychiatric Emergency Care (PEC) services – which provide acute medical and psychiatric care 24 hours per day/7 days per week. The PEC is staffed by a psychiatry resident, psychiatric social worker, and a VA psychiatry attending.

A clinical warning indicating participation in this research study will be added to the participant's CPRS medical record. The clinical warning will be removed when the participant completes study involvement.

PAYMENTS TO SUBJECTS

Subjects will be paid \$75.00 for each study visit (six study visits total, or \$450.00 total if a subject completes all six study visits). If a subject attends two study visits, the subject will be paid \$150; if s/he attends 3 study visits, will be paid \$225, etc.). There are no research-related costs to subjects participating in this study. Participants will be paid by direct deposit or provided with a paper voucher, which is redeemable for cash at the Durham VAMC Cashier's Office (payment for funds will be provided by the VA, as this study is funded by a VA Career Development Award).

There will be an additional allowance for travel to the Durham VAMC based on the distance traveled by the subject. The travel allowance will be approximated by the distance traveled. Travel allowance for several cities and major towns in VISN6 are included in the table below. There will be no further compensation for meals, parking, childcare, lost wages, etc.

Distance (roundtrip miles)	Allowance	Typical towns and cities
0-50	\$10	Raleigh, Durham, Cary, Chapel Hill
50-100	\$20	Henderson, Wake Forest, Burlington
100-200	\$30	Greensboro, Fayetteville, Goldsboro
200-300	\$40	Salisbury, Greenville, Rocky Mount
300-400	\$50	Wilmington, Charlotte, Hickory
> 400	\$60	

DATA AND SAFETY MONITORING

Sources of Materials

All of the data for this study will be collected specifically for research purposes. All study data will be kept in locked file cabinets, in locked offices within locked (card accessible only) buildings and will be accessible only to qualified research personnel [in Durham VAMC Building #5, Durham VAMC Building #15 (Room 405a), or VA MIRECC Building, third floor at [name]] . All locations are research controlled space). Each subject will be assigned a study number and all data and specimens will be identified by that study number. The list linking this number to subject identity will be kept in a file on a secure VA network drive

(S:\MIRECC\Research\[name] Study File), accessed through a password-protected computer to which only the Principal Investigator and study staff have access. Five sources of data will be maintained for this study and all collected information will be coded: a) the initial telephone screening, b) diagnostic interviews, c) physical examinations, d) psychiatric rating scales (both self-report and clinician-administered, e) neurosteroid profiles and other laboratory measurements.

Data Monitoring and Confidentiality

Reports from subjects' clinical records concerning research observations will not be made available to outside medical facilities without the written consent of the patient. All clinical and biological data obtained from research interviews and the laboratory will be coded. The coded data will be kept in locked file cabinets, in locked offices within locked (card accessible only) buildings and will be accessible only to qualified research personnel [in Durham VAMC Building #5, Durham VAMC Building #15 (Room 405a), or VA MIRECC Building, third floor at [name]]. Only study numbers will appear on data, documents and biological specimens used for evaluation or statistical analysis (ie, coded). The key-code linking subjects to study data identified by study number will be kept on a secure VA network drive (S:\MIRECC\Research\[name] Study File). In addition, any publications resulting from this research will not identify individual subjects.

PRIVACY AND CONFIDENTIALITY

Patient confidentiality will be maintained through the assignment of patient identification numbers. These numbers will be used in keeping of all research records. All hard copy research materials will be kept in locked file cabinets with keys available only to the principal investigator, and research personnel participating directly in this protocol. Patients will be informed during the consent process about the limits of confidentiality.

Information about study subjects will be kept confidential and managed according to the requirements of the Health Insurance Portability and Accountability Act of 1996 (HIPAA). Those regulations require a signed subject authorization informing the subject of the following:

- What protected health information (PHI) will be collected from subjects in this study
- Who will have access to that information and why
- Who will use or disclose that information
- The rights of a research subject to revoke their authorization for use of their PHI.

PHI collected as part of this study will include: name, address, telephone number, date of birth, dates of service, dates of attendance, social security number, gender, close relative's name, close relative phone number, marital status, race, education level, work status, employer, length of employment, occupation, service connection (reason, percentage), disability status, medical and mental health diagnoses and treatments, medication, substance use, history of suicide attempts, family history of suicide attempts, smoking status, incarceration history, twin status, military service (time period, branch, number of tours, whether or not subjects served in a war zone, fired a weapon in a combat situation, were under enemy fire, were wounded in a war zone, awarded medals or were prisoners of war). Genetic data and study visit and assessment dates will also be collected.

As part of the study (and as indicated in the HIPAA Authorization), patient information and medical and/or research records may be disclosed to the Office for Human Research Protections (OHRP), the VA Office of the Inspector General (OIG), the Office of Research Oversight (ORO), other government agencies, the Durham VAMC Institutional Review Board (IRB), and/or local Research Compliance Officers, and Food and Drug Administration (FDA).

In the event that a subject revokes authorization to collect or use PHI, the investigator, by regulation, retains the ability to use all information collected prior to the revocation of subject authorization. For subjects that have revoked authorization to collect or use PHI, attempts will be made to obtain permission to collect at least vital status (i.e., that the subject is alive) at the end of their scheduled study period.

INFORMATION SECURITY

Collection, Use and Storage of Research Information

Participant data will be stripped of HIPAA identifiers listed in Appendix B of the VHA Handbook 1605.1 (except for study date), and participant information will be identifiable only by a unique, linked numerical code (i.e., coded data). The master key code will be maintained on the secure VA network drive (S:\MIRECC\Research\[name] Study File) and which is accessible only through a VA, password protected computer [in Durham VAMC Building #5, Durham VAMC Building #15 (Room 405a), or VA MIRECC Building, third floor at [name]]. All electronically recorded PHI (i.e., any patient identifying information) will be maintained on a secure VA password protected network drive (S:\MIRECC\Research\[name] Study File) on a VA computer. Any PHI collected on paper which needs to be maintained (ie, Informed Consent Form, HIPAA Authorization, Subject Payment Forms, etc) will be stored in a folder separate from coded paper forms (i.e., study assessments). These two folders will be filed in two different locked file cabinets inside a locked room within the Durham VAMC [in Durham VAMC Building #5, Durham VAMC Building #15 (Room 405a), or VA MIRECC Building, third floor at [name]]. Only approved VA researchers and study personnel will have access to this information. No PHI will be removed from the Durham VAMC environment. Coded information collected using paper forms (i.e., study assessments) will be stored in a locked filing cabinet [in Durham VAMC Building #5, Durham VAMC Building #15 (Room 405a), or VA MIRECC Building, third floor at [name]]. These paper forms will be entered into a database stored on a separate, secure, password protected database (S:\MIRECC\Research\Datasets\[name]\Pain Preg Data Files) within the Durham VAMC (so that information cannot be linked to participant PHI) by study personnel and will be stored indefinitely according to VA guidelines. Paper form and electronic data will be destroyed in accordance with the Records Control Schedule.

Patient blood and serum samples will be collected during the study visit(s) and coded with a corresponding unique, linked numerical code (ie, the study ID number). Coded blood and serum samples will be stored at the Durham VAMC in a locked freezer room in Building 6 or Building #15 located in secure research wings (requires special permission and a security activated badge to gain access) within the Durham VAMC. At different points, a small portion of this blood will be hand-carried by study personnel to Duke University for the purposes of pharmacogenetic and genetic analysis only. Any remaining samples will be returned to the Durham VA after analyses have been completed. Data derived from blood and serum samples will be returned to the VA thru a VA-issued encrypted thumb drive.

Subjects will be asked to provide permission to store their contact and demographic information and study interview results in a secure database (an excel spreadsheet maintained by the PI and her study staff on a secure VA server) to be used to select potentially eligible participants for other ongoing and future studies. If patients provide permission to do so, they may then be re-contacted in the future and invited to participate in other studies for which they may qualify, and of which Drs. [name] and/or [name] are investigators. Demographic information asked will include: name, social security number, birthdate, gender, address, telephone number, close relative's name, close relative phone number, marital status, race, education level, work status, employer, length of employment, occupation, service connection (reason, percentage), disability status, history of hospitalization for schizophrenia, schizoaffective disorder or PTSD—if yes, age of diagnosis, family history of schizophrenia or schizoaffective disorder, history of suicide attempts, family history of suicide

attempts, smoking status—if yes, age of start, or quit, incarceration history, twin status, military service (time period, branch, number of tours, whether or not subjects served in a war zone, fired a weapon in a combat situation, were under enemy fire, were wounded in a war zone, awarded medals or were prisoners of war).

Any incident regarding theft/loss of data, authorized access of sensitive data or storage devices or non-compliance with security controls will be addressed according to VA policy (VHA Handbook 1200.05, 10j; 1058.01 11.a; 6500, Appendix D and 6500.2) and will be reported to Durham VAMC PO and ISO immediately using the following: [contact].

Study members who are initially part of the study team, but leave the study team for whatever reason will no longer have access to participant study data.

DATA ANALYSIS AND STATISTICAL CONSIDERATIONS

Statistical Methods

Analysis of treatment effects will use the mixed-models approach to repeated-measures analysis of variance (SAS Institute, Cary, NC) with baseline and endpoint scores as dependent variables, time as a within-subject repeated measure, and treatment group (pregnenolone or placebo) as a between-subjects fixed factor. The primary analyses for this will be based on an intention-to-treat principle that will include in the analyses all randomized subjects. The primary efficacy outcome variable is the weekly mean of the average pain scores (0 – 10 numeric rating pain score recorded daily from patient) after study drug initiation. These are obtained over time, and thus we will use mixed effects models with random intercepts to account for subject effects and the correlation among repeated measurements within a subject. Models will be developed which include as independent variables the treatment group and the baseline pain score. Thus, the effect of the intervention will be assessed by examining the significance of the slope β_1 coefficient for intervention in the following model:

$$P_{it} = \beta_0 + b_{0i} + \beta_1 Int + \beta_2 BaseP + \beta_3 t + e_{it}$$

where P_{it} is the mean weekly pain score for the i^{th} individual at time point t , β 's denote fixed effects, b_{0i} is the random intercept for the i^{th} individual, and e 's are random errors. Patients who are withdrawn from the study because of side effects will only be included in outcome assessments in which they participated. The mixed effects models can handle incomplete panels of information. All tested hypotheses will be considered statistically significant if the 2 sided p value is ≥ 0.05 unless otherwise specified.

Secondary analyses will include the following assessments. Assessment of changes in mood, anxiety, sleep, working memory, executive function, and pain interference (BDI, DTS, Tower of London, Digit Sequencing Task, BPI interference, PGI, AIS) will be analyzed via a repeated measures analysis similar to analyses for primary outcome assessments. Categorical analyses of patient response (30% improvement, 50% improvement) will be evaluated via a comparison of proportions using Fisher's exact test. Time to event analyses will also be performed, to examine the time to 30% and time to 50% reduction in 24 hour average pain score, using daily pain score data. These analyses will be performed by calculating Kaplan-Meier survival curves. Changes in physical function, mental health, cognitive symptoms and back pain-related disability will be assessed using ANCOVA models. Safety will be assessed by comparing the incidence of major and minor side effects (defined in human subjects section below) in the study drug vs. placebo groups, using Fisher's exact tests. Path analysis will be used to perform a preliminary assessment of whether any pain reduction effect is independent of possible effects of study drug on anxiety and mood.

Missing data: The mixed models used to evaluate the continuous response variables are able to handle moderate amounts of missing data provided they are missing at random. We will examine the missing at random

assumption by assessing differences between dropouts and completers on baseline as well as response variables up to point of premature withdrawal. If the missing at random assumption does not appear to be tenable, we will report the mixed models results but spend additional effort characterizing treatment effect at time of premature withdrawal.

[figure not shown]
Power Analysis and Sample Size Determination:

The effect of pregnenolone on low back pain will be evaluated using several statistical methods. This clinical trial design will compare two randomly assigned groups (pregnenolone or placebo) with respect to self-reported lower back pain measured on a 0-10 pain scale. Inclusion criteria for the study require that all participants report pain severity of at least 4/10. Given the low back pain often presents as long periods of low-level intensity pain punctuated by periods of acute exacerbation, it is quite likely that the mean pain level for selected participants will substantially exceed 4/10. Thus for power calculations, we assume a baseline mean pain level of six for each group. We also assume a standard deviation of 1.0 since we have little information to support any specific value in this population.

For the purpose of power calculations we assume that the mean pain levels of the two independent groups will be compared using a Two-Sample T-Test, Null Hypothesis: $\text{Mean1}=\text{Mean2}$. Alternative Hypothesis: $\text{Mean1}<>\text{Mean2}$. The standard deviations were assumed to be unknown and equal.

Assuming specified numbers of participants in each group (N) the mean differences detectable for at least 80% power and $\alpha=0.05$ are shown in the following table and figure.

N1	Mean1	Mean2
4	6.0	3.6
5	6.0	3.8
6	6.0	4.0
6	6.0	4.2
8	6.0	4.4
10	6.0	4.6
12	6.0	4.8
17	6.0	5.0
26	6.0	5.2
45	6.0	5.4
100	6.0	5.6

Group sample sizes of 45 achieve at least 80% power to detect a difference of 0.6 between the null hypothesis that both group means are 6.0 and the alternative hypothesis that the mean of group 2 is 5.4 with estimated group standard deviations of 1.0 and 1.0 and with a significance level (alpha) of 0.05000 using a two-sided two-sample t-test. Using this experimental group size should yield sufficient power to detect clinical meaningful effects.

Data Collection: Data pertaining to psychiatric rating and other assessment scales will be collected on hard copy and data pertaining to laboratory values will be collected in manners used for the VA Mid-Atlantic MIRECC Registry. A study number identifying clinical and biological data will be the only number to appear on data and documents used for evaluation or statistical analysis. This data will be kept in locked file cabinets accessible only to qualified personnel.

REFERENCES

